8.2 Handling of Biospecimens Collected for Correlative Research

Biospecimens collected for this study will be stored in the Lineberger Comprehensive Cancer Center (LCCC) Tissue Procurement Facility (TPF), or if needed, in a secure off-site storage facility. All biospecimen samples will be obtained in accordance with procedures outlined in the LCCC 2119 Study Laboratory Manual and stored in containers with controlled access. Each sample will be assigned a unique code number and no identifiable personal health information (PHI) will be on the specimen label. Information about the subject's disease will be linked to the specimens stored in the repository database. TPF-associated research staff, LCCC Bioinformatics staff who support the TPF database and the LCCC Data Warehouse, and researchers with IRB-approval for access to PHI for each subject in this study will be able to link specimens to relevant medical information. Some results from laboratory analyses that occurred during the subject's participation in the clinical study may also be included. This information may be important for understanding how the subject's cancer developed and responded to treatment.

Storage Time:

- The biospecimen will be used first and foremost for research purposes outlined within the confines of this protocol. Samples will be discarded/destroyed after relevant data are collected for this study, unless consent was obtained from the subject to use tissue for other research purposes (e.g., TPF consent form was signed by the subject). In this circumstance, there is a 15-year limit on use and storage of the biospecimens. If storage is anticipated to be indefinite, there will be an opt-out on the informed consent form allowing subjects to choose not to allow their specimens to be used for such future research.
 - The investigator must agree to abide by policies and procedures of the TPF facility and sign a letter of research agreement for ethical and appropriate conduct of their research that utilizes specimens obtained from the TPF facility (e.g., Use of leftover specimens will require a protocol outlining the research plan for biospecimen use).

Compliance Statement

Biospecimen collection for this study will be conducted in full accordance with all applicable University of North Carolina (UNC) Research Policies and Procedures and all applicable Federal and state laws and regulations including 45 CFR 46, and the Health Insurance Portability and Accountability Act (HIPAA) Privacy Rule. Any episode of noncompliance will be documented.

The investigators will perform the study in accordance with this protocol, will obtain consent, and will report unexpected problems in accordance with The UNC IRB Policies and Procedures and all federal requirements. Collection, recording, and reporting of data will be accurate and will ensure the privacy, health, and welfare of research subjects during and after the study.

Provision of Data to Correlative Scientists

Identification and Role of the Study Coordinator (or other named role) as the Honest Broker

The study coordinator (or other named role) will be in charge of collecting and maintaining all data points and data management. The study coordinator should have adequate training to enter, manage, and deidentify data. The study coordinator will provide a unique study number to each enrolled subject. All documentation and samples will be labeled with the unique study number. The correlative teams will only be provided this unique study ID number as opposed to any other patient identifiers. The clinical team will be the only people able to access identifiable data and the study coordinator will be a conduit to provide the de-identified data to the correlative team.

Requests for a data

Identifiable data will not be given out to any correlative investigators at any time. Multicenter and UNC correlative Investigators may ask the study coordinator for a specific data set, and the study coordinator will return a deidentified data set. This data may only be used for purposes of the study. Any use other than directly related to the study must be approved by the IRB of record. If there is a need for an investigator to access identifiable data during the study, then a new IRB application will need to be submitted from that investigator detailing the reasons needed to access that data. The study coordinator will also ensure that correlative results are not returned from the correlative team to the clinical team to dictate treatment or follow-up decisions unless this is specifically approved by the IRB of record and delineated in the clinical protocol.

8.3 Assessment of Safety

Any subject who receives at least one dose of study therapy on this protocol will be evaluable for toxicity. Each subject will be assessed periodically for the development of any toxicity according to the Time and Events Table. Toxicity will be assessed according to the NCI CTCAEv5.0.

8.4 Assessment of Efficacy

Any subject who receives treatment on this protocol will be evaluable for efficacy. Subjects who are withdrawn from the protocol before receiving any study treatment will not be evaluated for efficacy and will be replaced.

To assess disease status, MM labs will be performed as a baseline prior to treatment and then as outlined in the Time and Events Table.

This study will use the Consensus Criteria for Response by the International Myeloma Working Group (IMWG) Appendix O. Response Criteria for Multiple Myeloma [51].

The primary endpoint of the study is overall response rate as defined as the percentage of subjects achieving a partial response or better (\geq PR) to study therapy at any time (per IMWG criteria provided in Appendix O. Response Criteria for Multiple Myeloma).

9.0 ADVERSE EVENTS

9.1 Definitions

9.1.1 Adverse Event (AE)

An adverse event (AE) is any untoward medical occurrence (e.g., an abnormal laboratory finding, symptom, or disease temporally associated with the use of a drug) in a subject or clinical investigation subject administered an investigational product and which does not necessarily have a causal relationship with this treatment. An AE can, therefore, be any unfavorable and unintended sign (including an abnormal laboratory finding), symptom, or disease temporally associated with the use of a medicinal product, whether or not related to the medicinal product.

Hospitalization for elective surgery or routine clinical procedures that are not the result of an AE (e.g., surgical insertion of a central line) need not be considered AEs and should not be recorded as an AE. Disease progression should not be recorded as an AE, unless it is attributable by the investigator to the study therapy.

9.1.2 Suspected Adverse Reaction (SAR)

A suspected adverse reaction (SAR) is any AE for which there is a *reasonable possibility* that the investigational product is the cause. *Reasonable possibility* means that there is evidence to suggest a causal relationship between the drug and the AE. A suspected adverse reaction implies a lesser degree of certainty about causality than adverse reaction, which means any adverse event caused by an investigational product.

Causality assessment to a study drug is a medical judgment made in consideration of the following factors: temporal relationship of the AE to study investigational product exposure, known mechanism of action or side effect profile of study treatment, other recent or concomitant drug exposures, normal clinical course of the disease under investigation, and any other underlying or concurrent medical conditions. Other factors to consider in considering drug as the cause of the AE:

- Single occurrence of an uncommon event known to be strongly associated with investigational product exposure (e.g., angioedema, hepatic injury, Stevens-Johnson Syndrome)
- One or more occurrences of an event not commonly associated with investigational product exposure, but otherwise uncommon in the population (e.g., tendon rupture); often more than once occurrence from one or multiple studies would be needed before the sponsor could determine that there is *reasonable possibility* that the investigational product caused the event.

- An aggregate analysis of specific events observed in a clinical trial that indicates the events occur more frequently in the investigational product treatment group than in a concurrent or historical control group

9.1.3 Unexpected AE or SAR

An AE or SAR is considered unexpected if the specificity or severity of it is not consistent with the applicable product information (e.g., Investigator's Brochure (IB) for an unapproved investigational product or package insert/summary of product characteristics for an approved product). Unexpected also refers to AEs or SARs that are mentioned in the IB as occurring with a class of investigational product or as anticipated from the pharmacological properties of the investigational product but are not specifically mentioned as occurring with the particular investigational product under investigation.

9.1.4 Serious AE or SAR

An AE or SAR is considered serious if, in the view of either the investigator or sponsor, it results in any of the following outcomes:

- Death;
- Is life-threatening (places the subject at immediate risk of death from the event as it occurred);
- Requires inpatient hospitalization (>24 hours) or prolongation of existing hospitalization; *
- Results in congenital anomaly/birth defect;
- Results in a persistent or significant incapacity or substantial disruption of the ability to conduct normal life functions;
- Important medical events that may not result in death, be life-threatening, or require hospitalization may be considered a serious adverse study treatment-related experience when, based upon appropriate medical judgment, they may jeopardize the subject or subject and may require medical or surgical intervention to prevent one of the outcomes listed in the definition. For reporting purposes, also consider the occurrences of pregnancy as an event which must be reported as an important medical event.

*Hospitalization for anticipated or protocol specified procedures such as administration of chemotherapy, central line insertion, metastasis interventional therapy, resection of primary tumor, or elective surgery, will not be considered serious adverse events.

Pregnancy that occurs during the study must also be reported as an SAE.

9.2 Documentation of non-serious AEs or SARs

For non-serious AEs or SARs, documentation must begin from day 1 of study treatment and continue through the 30-day follow-up period after treatment is discontinued.

Collected information should be recorded in the Case Report Forms (CRF) for that subject. Please include a description of the event, its severity or toxicity grade, onset and resolved dates (if applicable), and the relationship to the study drug. Documentation should occur at least monthly.

9.3 SAEs or Serious SARs

9.3.1 Timing

After informed consent but prior to initiation of study medications, only SAEs caused by a protocol-mandated intervention will be collected (e.g., SAEs related to invasive procedures such as biopsies, medication washout).

For any other experience or condition that meets the definition of an SAE or a serious SAR, recording of the event must begin from day 1 of study treatment and continue through the 30-day follow-up period after treatment is discontinued. NOTE: For drug(s) with long half-lives, it may be appropriate to extend the 30-day follow-up period.

9.3.2 Documentation and Notification

SAEs or Serious SARs must be recorded in the SAE console within OnCore® for that subject within 24 hours of learning of its occurrence. Additionally, the UNC Multicenter Project Manager must also be notified via email of all SAEs within 24 hours of learning of its occurrence.

9.4 Adverse Event Reporting

9.4.1 IRB Reporting Requirements

UNC:

- The UNC-IRB will be notified of all SAEs that qualify as an Unanticipated Problem as per the UNC IRB Policies using the IRB's web-based reporting system within 7 days of the Investigator becoming aware of the problem.

Multicenter sites:

- The IRB will be notified of all SAEs that qualify as an Unanticipated Problem in accordance with their SOPs. These events must be reported to the sponsor within 24 hours of learning of the occurrence and entered into OnCore® by the multicenter site.

Pregnancy

Pregnancies and suspected pregnancies (including a positive pregnancy test regardless of age or disease state) of a female subject occurring while the subject is on study, or within 30 days of the subject's last dose of study should be recorded as SAEs. The subject is to be discontinued immediately from the study.

For Affiliate sites, the pregnancy, suspected pregnancy, or positive pregnancy test must be reported to the Multicenter Project Manager immediately (within 24 hours) via email (preferred) or facsimile to [contact]. The Multicenter Project Manager will then report the event to the Funding Source (see requirements below). The female subject should be referred to an obstetrician-gynecologist, preferably one experienced in reproductive toxicity for further evaluation and counseling.

The Investigator will follow the female subject until completion of the pregnancy and must document the outcome of the pregnancy (either normal or abnormal outcome) and report the condition of the fetus or newborn to the UNC Project Manager. If the outcome of the pregnancy was abnormal (e.g., spontaneous or therapeutic abortion), the Investigator should report the abnormal outcome as an AE. If the abnormal outcome meets any of the serious criteria, it must be reported as an SAE.

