4.1.11 Male or Female Contraceptive Requirements

a) Male participants

Men must agree to use a latex or synthetic condom during sexual contact with a FCBP even if they have had a vasectomy from the time of signing the informed consent form through 90 days after the last dose of pomalidomide and 5 months after the last dose of isatuximab. These same patients must not donate sperm.

b) Female participants

A female participant is eligible to participate if she is not pregnant, not breastfeeding, and at least one of the following conditions applies:

Not a Female of childbearing potential (FCBP)*,

OR

If an FCBP, participant must have a negative serum or urine pregnancy test with a sensitivity of at least 25 mIU/mL within 10 – 14 days prior to and again within 24 hours of starting pomalidomide and must either commit to continued abstinence from heterosexual intercourse or begin TWO acceptable methods of birth control, one highly effective method and one additional effective method AT THE SAME TIME (Male or Female Contraceptive Requirements), at least 28 days before she starts taking pomalidomide through 90 days after the last dose of pomalidomide and 5 months after the last dose of isatuximab. FCBP must also agree to ongoing pregnancy testing during the entire duration of treatment and monthly for 5 months after the last dose of isatuximab. All patients must be counseled at a minimum of every 28 days about pregnancy precautions and risks of fetal exposure. All patients enrolled into this trial, must be registered in and must comply with all requirements of the POMALYST REMS program.

*A female of childbearing potential (FCBP) is a sexually mature female who: 1) has not undergone a hysterectomy or bilateral oophorectomy; or 2) has not been naturally postmenopausal for at least 24 consecutive months (i.e., has had menses at any time in the preceding 24 consecutive months).

4.1.12 Subject may be HIV+ if the following criterion are met:

1. CD4+ T-cell counts ≥ 350 cells/ μ L
2. No history of AIDS-defining opportunistic infections
3. Subject is on an established antiretroviral therapy (ART) for at least 4 weeks prior to initiation of study treatment.
4. Absence of known, clinically significant drug-drug interactions with isatuximab, pomalidomide, and dexamethasone.

4.1.13 Subjects is willing and able to comply with study procedures based on the judgement of the investigator or protocol designee.

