5.11 Off Study Criteria

Subjects will be considered off study by any of the following criteria:

- Death
- The subject completely withdraws from the study including any further data collection.
- The subject completes all study activities and follow up and no further data is to be collected.
- The subject is removed because of change of condition or other instance in which the investigator feels the subject is no longer able to complete the study.

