6.1.12.8 AESIs

An adverse event of special interest is an adverse event (serious or non-serious) of scientific and medical concern specific to the Sponsor's product

AESIs for isatuximab include infusion reactions (IRs), symptomatic overdose, secondary primary malignancies, viral reactivation, and pregnancy.

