Post-treatment visits will be conducted for subjects who have an ongoing \geq grade 3 or serious AE (SAE) at the end of treatment visit and will be continued until the event is resolved or deemed irreversible by the investigator. These visits will occur at least once every 4 weeks (± 1 week) for the first 6 visits and then once every 12 weeks (± 2 weeks) thereafter. However, follow-up every 12 weeks by telephone or any other modality is permissible if a less frequent monitoring schedule is clinically appropriate, and if the subject would otherwise require removal from the study.

In addition, post-treatment visits will be conducted for subjects who remain progression free at their end of treatment visit and will occur once every 4 weeks (± 1 week) for the first 6 visits and then once every 12 weeks (± 2 weeks) thereafter until disease progression or the start of a new MM treatment. If follow up of \geq grade 3 or serious adverse events (as outlined above) has also concluded, patients will then enter the long-term follow-up phase. If possible, during the post-treatment phase, subjects should complete the Karnofsky performance status, CARG global assessment, quality of life assessment, cognitive testing, and blood correlatives every six months until they enter the long-term follow up phase.

The Long-Term Follow-up period will begin (except in the case of withdrawal of consent) after the end of treatment and post-treatment (if applicable as outlined above) visits and will take place every 3 months

(±2 weeks) for a maximum of 3-years from the end-of-treatment visit. Long-Term Follow-up visits will be limited to history of any subsequent cancer treatments, diagnosis of another cancer and survival status. Long-term follow up assessments may be conducted either in person, by telephone, via audio/video, medical record abstraction, or by other modality deemed appropriate for this purpose by the investigator.

After documented progression of MM and/or initiation of other, non-study therapy, follow-up should be every three months by any modality (telephone, via audio/video, or by other modality deemed appropriate for this purpose by the investigator).

4. Hematology: CBC with white blood cell differential

5. Serum chemistries must include the following:

- Every chemistry assessment: sodium, potassium, chloride, CO₂, BUN, creatinine, glucose, and calcium.

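### The pregnancy recording rule in 9.4.1 (on study, or 30 days after last dose) does not match the 5-month post-treatment window in 4.1.11, and late viral reactivation has no stated collection rule for some subjects

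*Combined protocol and SAP*

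**What the plan says.** **Pregnancy.** Section 9.4.1 covers pregnancies "of a female subject occurring while the subject is on study" and those "within 30 days of the subject's last dose of study should be recorded as SAEs". Section 9.1.4 adds, with no day limit, "Pregnancy that occurs during the study must also be reported as an SAE". Section 4.1.11 sets contraception for men and women through 90 days after pomalidomide and 5 months after isatuximab, and requires testing in women of childbearing potential "monthly for 5 months after the last dose of isatuximab". Sections 5.6 and 6.1.12.3 repeat the 5 months. The pregnancy-test row of the Time and Events Table (8.1) has its last mark at end of treatment (EOT). Section 9.4.1 also takes a pregnant subject off the study at once, yet has the investigator follow her to the outcome of the pregnancy.

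**Events of special interest (AESIs).** Section 6.1.12.8 reads: "AESIs for isatuximab include infusion reactions (IRs), symptomatic overdose, secondary primary malignancies, viral reactivation, and pregnancy". Section 9.4.2.1 sends all serious events and AESIs to the funding source within 24 hours, with no end date. Sections 9.2 and 9.3.1 end site recording 30 days after treatment stops. Section 9.3.1 adds: "For drug(s) with long half-lives, it may be appropriate to extend the 30-day follow-up period".

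**Late contacts.** Footnote 3 of 8.1 states: "Long-Term Follow-up visits will be limited to history of any subsequent cancer treatments, diagnosis of another cancer and survival status". These contacts take place every 3 months for at most 3 years.

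**The concern.** The protocol asks women to be tested monthly for 5 months because it regards a pregnancy in that period as possible and important, but its explicit recording limit ends after the first of those months. A site could follow 4.1.11, find a positive test in month 3, and not know whether 9.4.1 requires a report. A site working from the schedule would not do the test at all. Two of the three drugs carry post-treatment contraception periods, and pomalidomide is under a restricted-distribution programme because of embryo-fetal risk (7.3.3). Few subjects in this older population are likely to be of childbearing potential, so the count would be small, but a missed exposed pregnancy is serious.

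The AESI question is similar. The duty to inform the funding source is open-ended, but it can only act on what sites collect.

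**Working it through.** The plan gives no figure to reproduce. The check is a comparison of sections with day arithmetic.

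**1. Recording limit against the testing window.**
Inputs: 30 days (9.4.1); 5 months after isatuximab with monthly tests, and 90 days after pomalidomide (4.1.11).
Assumptions: one month is 28 to 30.4 days, and the last isatuximab dose is also the last dose of study treatment.

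- Length of window: 5 × 28 = 140 days; 5 × 30.4 = 152 days.
- Outside the 30-day limit: 140 − 30 = 110; 152 − 30 = 122 days.
- Share covered: 30/140 = 21.4%; 30/152 = 19.7%.
- Monthly tests fall at about days 28–30, 56–61, 84–91, 112–122 and 140–152. One is at or before day 30; four are later.
- Pomalidomide: 90 − 30 = 60 days outside.

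If isatuximab stops before the other drugs, the uncovered isatuximab time shrinks by that gap.

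**2. Does the on-study limb close the gap?** Two readings are possible.

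- *On study means until off study under 5.11.* A subject who finishes normally is off study when "The subject completes all study activities and follow up and no further data is to be collected", up to 3 years after treatment. All 5 months are then covered, but the 30-day limb has almost no purpose: it would matter only for someone who leaves the study within 30 days of the last dose.
- *On study means on treatment.* The 30-day limb then has its natural role, and 110 to 122 days are uncovered.

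The text does not choose. The second reading gives every word of 9.4.1 a use; 9.1.4 leans towards the first.

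**3. Schedule.** EOT is within 30 days (±7) of the last dose (footnote 3), so a test there can serve as the first monthly test. The post-treatment and long-term columns of the row are blank. Footnote 1d calls for monthly tests after the first 4 weeks of therapy and does not mention the 5 months after isatuximab.

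**4. Partners.** Section 9.4.1 names female subjects only. Section 4.1.11 puts men under the same 90-day and 5-month limits. No section expressly tells a site to record or follow a partner's pregnancy.

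**5. Leaving the study.** Section 5.8 lists pregnancy as a reason to end treatment. Section 9.4.1 says the subject leaves the study. Section 5.11 lists removal by the investigator among the ways to be off study. Section 9.4.1 then requires follow-up to outcome.

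**6. Late AESIs, by type of subject.**

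| At EOT | Next contact | Viral reactivation | Second cancer |
|---|---|---|---|
| Progression-free, or ongoing grade ≥3 or serious event | Post-treatment visits about every 4 weeks for the first 6, then 12-weekly; toxicity assessment marked | Could surface, but 9.2 and 9.3.1 have ended recording at day 30 | Could surface there; asked later in long-term follow-up |
| Progressed, no such event | Long-term follow-up, 3-monthly | Not asked | Asked, up to 3 years |

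The table marks medical history in the long-term column, but footnote 3 confines it to three items. Section 5.5 addresses viral reactivation only during treatment. No section says that a second cancer learned of at these contacts goes out as a 24-hour AESI.

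**The case against.** The best defence is that several routes remain open. Section 9.4.1 has an on-study limb as well as the 30-day one, 9.1.4 sets no day limit and is not restricted to female subjects, 9.4.2.1 has no end date for AESIs, and 9.3.1 permits a longer window. Footnote 1d gives no stop date for monthly tests, and every patient is bound to the pomalidomide REMS. This stands as far as it goes: it shows that reporting is possible, not that it is required. The on-study term is undefined, the extension has no length or trigger, and the documents do not give REMS reporting rules for the months after treatment. On leaving the study, the specific duty to follow the pregnancy is clear enough; the conflict is one of wording.

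A reader might infer more than the text supports:

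- *Second-cancer collection stops at 30 days.* It does not; footnote 3 collects other cancers for up to 3 years.
- *About 2 of 49 second cancers would be lost.* Section 6.1.12.6 gives 3.9% on isatuximab, and 0.039 × 49 = 1.9, but that is an expected total. The documents give no rate after day 30. Four of the six cited cases were skin squamous cell carcinoma, and those patients continued treatment after resection.
- *Five months is a general isatuximab risk window.* It is a contraception and pregnancy-testing window and says nothing about cancers or reactivation.
- *AESI rates would be biased low by design.* No AESI rate is a planned estimate; the safety endpoint in 3.2.1 is treatment-related adverse events.

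**Conclusion.** The sections conflict and should be corrected. On the reading that gives the 30-day limb a purpose, about four fifths of the protocol's 5-month window, and about 4 of 5 required tests, lie outside the explicit rule for recording a pregnancy. This rests on the month length and common last dose assumed above. On the broader reading of on study nothing is lost, but sites cannot tell which reading applies. Whichever is meant, the schedule omits tests that 4.1.11 requires, and 9.4.1 leaves out partner pregnancies.

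The AESI part is narrower. Viral reactivation has no late question for subjects who stop for progression without an ongoing grade 3 or higher or serious event, and late second cancers are collected without a stated reporting route. The documents do not show that such events would go unreported, and the number affected cannot be estimated from them. Efficacy inference is untouched.

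**What to change.** - In 9.4.1, replace the 30-day limit with the post-treatment window in 4.1.11, say what on study means, and state that pregnancies in partners of male subjects are included. Section 4.1.11 joins the pomalidomide and isatuximab limits with *and*, whereas 5.6 joins them with *or* for women; these should be reconciled at the same time.
- Add the post-treatment pregnancy tests to the Time and Events Table and footnote 1d.
- Reconcile the removal wording in 9.4.1 with 5.8, 5.11 and the follow-up to pregnancy outcome.
- In 9.3.1 and footnote 3 of 8.1, state that second cancers and viral reactivation learned of at the existing post-treatment and 3-monthly contacts are reported as AESIs, and add viral reactivation to what the long-term contact asks. Thirty days can stay for other events.

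The cost is wording, one added question at contacts that already take place, and slightly more safety reporting. The tests are already required by 4.1.11, but women who have progressed have no monthly visit, so sites would need to arrange them. Sample size, error rates and the efficacy analysis do not change.
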